## 2.4. Eltrombopag

Eltrombopag (SB-497115-GR, Promacta®), the bis-monoethanolamine salt form, is an orally bioavailable, small molecule 2nd generation thrombopoietin receptor (TPOR) agonist, developed for the treatment of thrombocytopenia by scientists at GlaxoSmithKline (now Novartis) (45). Studies conducted in vitro have shown that eltrombopag is an effective agonist binding to TPOR, the TPO receptor encoded by the *MPL* gene, to stimulate thrombopoiesis. It binds TPOR at a position distinct from the ligand binding site, within the juxtamembrane domain of the receptor, and thus does not compete with TPO for binding to its receptor (46). The differences in binding to the receptor may theoretically result in activation of different signaling pathways from native TPO, however, data indicate similar impact on megakaryocytes and stem cells comparing EPAG to TPO (47).

*In vivo*, EPAG increased platelet numbers in chimpanzees (the only non-human species which is pharmacologically responsive to eltrombopag) (47). These findings, coupled with supporting clinical efficacy data in humans, suggested that eltrombopag is an orally active TPO-R agonist that functions in a similar manner to endogenous TPO. Initial clinical trials were carried out in normal volunteers, and then in patients with chronic ITP, based on their inappropriately low or low-normal levels of endogenous TPO (48). The initial phase I/II and randomized, controlled phase 3 registration trials in chronic ITP were very encouraging, with little toxicity and much higher responses in comparison with placebo (49-51), which led to its approval by the Food and Drug Administration (FDA) on November 20, 2008 for patients with chronic ITP who have had an insufficient response to corticosteroids, immunoglobulins, or splenectomy. Eltrombopag was the first oral TPO-R agonist approved for adult patients with chronic ITP. In November 2012, FDA approval was received for hepatitis C associated thrombocytopenia.

[figure not shown]
In analogy to TPO, EPAG appears to stimulate HSC proliferation and self-renewal, and was thus utilized by our group in a clinical trial for patients with refractory acquired SAA and shown to result in clinically-meaningful responses in about 50% (52, 53). Furthermore, the fact that the responses were sustained even after EPAG was discontinued supports its direct effect on the stem cell compartment in SAA patients. Based on these results in patients with SAA, EPAG was FDA approved for refractory SAA in August 2014, at an adult dose of 150 mg/day, higher than the doses utilized in ITP (52, 53). TPO levels are already markedly elevated in SAA patients, suggesting additional mechanisms leading to HSC expansion with EPAG treatment. Although EPAG's function appears to be dependent on TPOR, it may activate the receptor differently than endogenous TPO (54-56). The different activation may result in the activation of distinct pathways favoring HSC fitness. Indeed, differences in signaling pathways between TPO and eltrombopag have been observed in platelets (47). In addition, our recent investigations indicate that EPAG can bypass the inhibitory effect of IFN- $\gamma$  on TPOR signaling (57).

Longer follow-up in the ITP EXTEND trial (NCT00351468) suggests that eltrombopag remains well tolerated. On December 6, 2011 Novartis announced that the FDA agreed to modify eltrombopag's Risk Evaluation and Mitigation Services designed to assure safe use of the novel agent and removed the requirement for healthcare professionals and institutions to enroll in the Promacta Care Program (Promacta® Package Insert, 2011). Monitoring of adverse events for eltrombopag will be continued via post-marketing surveillance programs and ongoing clinical trials, rather than a formal prescriber enrollment program. There has been no suggestion of an increased risk of myelodysplasia or any other clonal bone marrow disorder in patients treated on the EXTEND Trial for ITP.

2.4.1. Eltrombopag improves trilineage hematopoiesis in a TPOR-independent manner

The trilineage response of patients to EPAG, despite the drug being an agonist directed primary towards the megakaryocytic lineage, suggests that EPAG may have multiple effects *in vivo*. Work by Kao *et al.* is of particular note as they demonstrated that EPAG is capable of stimulating hematopoietic stem cells in mice (59). This is notable because prior work has clearly demonstrated that the mouse receptor does not bind EPAG. Furthermore, romiplostim, an unrelated TPOR agonist, does not have this effect in mice. These results are suggestive of an EPAG-specific mechanism, independent of the TPOR found on megakaryocytes and primitive stem cells. For example, recent work by Guenther *et al.* has suggested that EPAG may improve hematopoiesis by improving the DNA damage response in hematopoietic cells (60). Others have examined the interaction of EPAG with the inflammatory milieu (57).

#### 2.4.2. Eltrombopag has clinically significant iron chelation activity *in vivo*

However, it is the iron-binding capabilities of EPAG that present the most promise for DBA patients, and likely explain the effects seen in our patient. Our work with EPAG has shown that it is capable of mobilizing intracellular iron and acting as a potent chelator, with patients on EPAG long-term dropping levels of storage iron over time (61). Indeed, EPAG has demonstrated a higher affinity for iron than clinically available chelators (62, 63). EPAG can mobilize iron from multiple different cell types at clinically relevant concentrations. Notably, EPAG can mobilize bone marrow iron observed in transfusion-related iron overload (64). Both orally available chelators (deferasirox and deferiprone) are also able to penetrate the cellular membrane due to their smaller size and chemical properties unlike deferoxamine (65-68). As such these agents are believed to have some intracellular chelation activity, especially within the heart, but this activity is highly variable, tissuedependent, and secondary to their main mechanism of action (69, 70). Indeed, continuous infusion deferoxamine remains the highly effective gold standard in the treatment of cardiac hemochromatosis despite its lack intracellular activity. These different agents are reviewed in (71). Therefore, a more potent intracellular chelator could have significant clinical impact.

Our own experiences with EPAG have confirmed that it is a potent chelator of iron and can mobilize whole body iron stores even in transfusionally iron-overloaded patients (61). Specifically, in patients on EPAG for at least 4 months, whole body iron as measured by serum ferritin was decreased, especially in patients treated on an extended access protocol (Figure 2), including our index DBA patient (Figure 1D). Paradoxically, in patients being treated with EPAG, serum iron levels are actually elevated, reflecting the mobilization of the intracellular iron into the blood stream, from which it is ultimately cleared and lost via hepatic processing of the iron-bound drug. Indeed, in several patients treated on extended doses of EPAG (average 2 years of drug exposure), iron supplementation was required due to the development of iron deficiency anemia in the face of an otherwise strong response to EPAG. Several investigations into the metabolic effects of EPAG in cells have demonstrated that through the depletion of iron, there is a concomitant reduction in the toxic reactive oxygen species (59, 63, 72, 73).

**Figure 2: Impact of eltrombopag upon iron stores in patients treated for aplastic anemia.** (A) Ferritin levels in patients with EPAG treatment for at least 4 months. (B) Comparison of ferritin levels pretreatment and after EPAG discontinuation in 6 patients with prolonged EPAG treatment and ferritin measurements available at follow-up. Student's *t* test: \*\**P* = .005 (61)

Given these findings of intracellular iron depletion, improvement in reactive oxygen species levels, and the clinical response we have previously seen in our DBA patient, we hypothesize that through its iron chelating properties, likely in combination with its stimulatory effects upon TPOR, EPAG may be able to offset the toxic effects of aberrant hemoglobin biosynthesis in DBA patients, increasing erythroid production, and ultimately allowing HSC self-renewal, thus improving anemia, preventing the long-term hematologic consequences of DBA, and even avoid the significant toxicities of transplant. By chelating and subsequently removing total body iron effectively, we hypothesize that EPAG will also improve organ function and overall long-term outcomes in DBA patients previously experiencing iron overload as a consequence of prior transfusion therapy.

## 2.4.3. Rationale for dose selection

Eltrombopag 150 mg once daily in adults or the equivalent in children has been selected as the starting dose for this study because this dose regimen has been safe and effective in increasing platelet counts in our recently-completed non-randomized, off label, phase II study (NCT00922883) of EPAG as a single agent in patients with refractory SAA. Forty-three (43) patients (age range 18-77 years) received 50 mg daily of EPAG with dose escalation every two weeks to a maximum dose of 150 mg daily. Patients were successfully escalated to the 150mg daily dose without dose-limiting toxicities. Hematologic responses

were only observed while patients were receiving the 150mg daily dosing. While it is possible that patients would have responded to lower doses of drug had the dose not been escalated every two weeks, the lack of toxicity at the 150 mg/day dose in the prior study supports our rationale for utilizing this dose throughout the current trial, unless dose modifications based on toxicity or response criteria are required. A starting dose of 75 mg once daily in East Asian and South East Asian patients will be used. Modified dosing for subjects of East Asian and South East Asian heritage (self-reported) has been implemented for the following reasons. In healthy Japanese subjects, plasma eltrombopag AUC(0- $\tau$ ) was approximately 80% higher when compared with non-Japanese healthy subjects who were predominantly Caucasian. Similarly, in patients with ITP, plasma EPAG levels were approximately 70% higher in East Asian and South East Asian subjects as compared with non-East Asian subjects who were predominantly Caucasian. Similarly, is patients with ITP, plasma EPAG levels were approximately 70% higher in East Asian and South East Asian subjects as compared with non-East Asian subjects who were predominantly Caucasian as higher drug exposure in East Asian and South East Asian subjects has been observed.

The most extensive data on dosing and long-term side effects have been obtained in patients with chronic ITP. An initial randomized phase 2 trial, followed by two randomized phase 3 trials all showed efficacy for EPAG compared with placebo for increasing the platelet count utilizing doses of up to 75 mg per day (49, 50, 74). In ITP subjects, there was a dose response for EPAG 30 mg to 75 mg once daily, with geometric mean AUC(0- $\tau$ ) values of 169 µg/mL for the 75 mg once daily regimen. There was no significant difference between the safety profile of ITP subjects receiving 30, 50 or 75 mg of EPAG. A recent update of the EXTEND study reported on 302 patients followed up to 5.5 years on EPAG therapy for chronic ITP, with a median exposure of 121 weeks and median dosing of 51.4 mg/day. Forty-three (43) patients (14%) discontinued therapy due to adverse events, including headaches, thromboembolic events, or hepatobiliary laboratory abnormalities. An independent central pathology review of bone marrow biopsies did not reveal significant increase in reticulin deposition.

Thrombocytosis is a theoretical risk of EPAG treatment when high dosages are administered. However, thrombocytosis has not been observed in the 43 patients with refractory SAA who were treated with 150 mg per day nor in any of our other EPAG protocols (09-H-0199, 11-H-0134, 12-H-0150 and 13-H-0133). Thrombocytosis has been observed in healthy volunteers as well as in subjects with ITP, and there was a suggestion of a higher risk of thrombosis in patients on EPAG compared with placebo in the phase III randomized trials for chronic ITP(50). However, patients with ITP, in contrast to patients with DBA, have hyper-reactive platelets and an increased endogenous risk of thrombosis. In an extensive analysis of ITP patients treated long-term with romiplostim, an alternative TPO mimetic, there was no evidence for increased thrombotic events in the romiplostim-treated patients compared with controls (75). In a meta-analysis of randomized trials using either EPAG or romiplostim, there was a numerically but non-statistically significant trend

to increased occurrence of thromboembolisms compared with controls (76). In the current trial, based on concerns regarding thrombosis, dose reductions of EPAG will be made if the platelet count reaches  $600,000/\mu$ L or greater.

# 2.4.4. Rationale for pediatric dose selection

For pediatric subjects, there is a predicted higher weight-adjusted drug clearance than older children and adults based upon studies of several drugs approved for use in children, such as anticonvulsants, proton pump inhibitors, theophylline, and HIV protease inhibitors, have routinely demonstrated that young children have higher weight-adjusted drug clearance than older children and adults (77-81). In the PETIT trial, a phase II pediatric chronic ITP study, subjects between 1 and 5 years received a mean average daily dose of 2.2 mg/kg EPAG (mean max 2.9mg/kg), while subjects between 6 and 11 years of age received an average daily dose of 54.8 mg daily while subjects aged 12-17 year received 57.3mg EPAG. The maximum dose used in the PETIT trial among all age groups is 75 mg daily. Non-Asian patients aged 1-5 years, that were treated in the subsequent randomized, multicenter, placebo-controlled study PETIT2, started with 1.2 mg/kg/day. The median average dose per day was 3.4mg/kg (42.8 mg) in this cohort and 56.9mg/kg in patients aged 6-11 years. Non-East Asian patients aged 12-17 years were treated with a median average dose per day of 69.0 mg. No new pediatric specific safety signal has been identified thus far.

An analysis of combined pharmacokinetic data from the PETIT and PETIT2 trials, encompassing 168 pediatric patients with ITP aged 1 year and older, demonstrated that clearance increases with body weight. Notably, patients in the 1-5 year age group experience approximately 60% higher exposure to drug (AUC(0-τ) 162 µg·hr/mL 95% CI: 139-187;  $C_{max}$  11.6 µg/mL 95% CI: 10.4-12.9) compared with adults (AUC(0-τ) 101 µg·hr/mL 95% CI: 91.4-113;  $C_{max}$  7.03 µg/mL 95% CI: 6.44-7.68); whereas teenagers, aged 12 to 17 years, experience exposure (AUC(0-τ) 103 µg·hr/mL 95% CI: 91.1-116;  $C_{max}$  6.80 µg/mL 95% CI: 6.17-7.50) comparable to adults. Older children and pre-adolescents, aged 6 to 11 years, experience an intermediate exposure (AUC(0-τ) 153 µg·hr/mL 95% CI: 137-170;  $C_{max}$  10.3 µg/mL 95% CI: 9.42-11.2) that is nonetheless similar to toddlers and young children (82).

The available platelet count, safety, and PK data available for subjects enrolled in the PETIT trial support a starting dose of 2.5 mg/kg once daily for non-East-Asian subjects aged 2-5 years (82-84). Older pediatric patients will start at a fixed total dose; however, as they are expected to experience a higher pharmacologic exposure compared to adults, the starting dose for non-East-Asian subjects, aged 6-11, will be 75 mg daily. Patients 12 years and older will start at the adult dose of 150 mg daily.

#### 2.4.5. Rationale for permitting dose interruption

The effect of dose interruption is unknown in the DBA population. Thirty-one percent (34 ITP subjects) on the long-term extension study (EXTEND Trial, NCT00351468) had an interruption to EPAG dosing at some point in the study. Of the subjects requiring a dose interruption, 7 had a dose interruption lasting 1 to 7 days and 27 had a dose interruption lasting greater than 7 days. Platelet counts decreased back to baseline within 1-2 weeks, although not associated with any bleeding complications. However, the underlying pathophysiology of thrombocytopenia in ITP is very different from DBA or SAA, and EPAG is being utilized in that disorder to overproduce platelets in the bone marrow to compensate for increased and ongoing antibody-mediated platelet destruction. In DBA, we postulate an effect on HSCs in the bone marrow, and a much more prolonged effect from EPAG; therefore, our prediction would be that short or even longer-term dose interruptions will not result in any sudden changes in blood counts. We would anticipate some patients on the current trial might have dose interruptions due to intervening illnesses such as gastroenteritis, and may require suspension of the study drug temporarily.

2.4.6. Rationale for treatment duration (primary endpoint 6 month), extended access to EPAG for responding patients and slow tapering of EPAG during this extension part of the study

Eltrombopag is safe and relatively non-toxic with prolonged use. The EXTEND study (NCT00351468), an open label dose modification extension study evaluating the safety and efficacy of extended therapy of EPAG in ITP subjects, has been designed to assess long-term effects of EPAG therapy. At the most recent analysis of 302 patients (presented at EHA, 2016) the median average daily dose was 50.4 mg. The median duration of exposure to EPAG was 2.4 years (range, 2 days to 8.8 years). EPAG was well-tolerated, and both bleeding and clinically-significant bleeding decreased from baseline at all time points. AEs and SAEs occurred in 92% and 32% of patients respectively. SAEs considered possibly drug-related occurred in 8% of patients. AEs leading to withdrawal occurred in 14% of patients. The most frequent AEs leading to withdrawal were increased ALT (n=5), increased bilirubin (n=4), cataracts (n=4), and DVT (n=3). Nineteen patients (6%) reported thromboembolic events (TEEs), and 37 reported hepatobiliary laboratory abnormalities. ITP patients have return of their platelet counts to baseline within 1-2 weeks of discontinuation of drug.

In our cohort of 43 patients treated for refractory severe aplastic anemia (SAA), responses only began to be observed at the 3-month time point, and with continued exposure to drug, blood counts of all lineages improved towards the normal range gradually. Maximal response was not reached at 6 months with bone marrow cellularity normalizing by 9-15 months. Eighteen of 43 patients with refractory SAA had drug discontinued for robust response. Only 2 patients showed a decrease in counts clearly related to the discontinuation of EPAG. Re-initiation of EPAG restored hematopoiesis in both patients. However, EPAG was discontinued in one patient because of an intermittently detected cytogenetic abnormality. Since then the counts have remained stable and a repeat bone marrow biopsy showed a normal karyotype. These results suggest that the effect of EPAG on HSPC number or function is long-lasting and prolonged therapy may not be required in SAA.

In patients with DBA the HSPC potential is also reduced but, unlike acquired BMFS, HSPC in subjects with DBA carry inherited mutations impacting hemoglobin synthesis (§2.1). Assuming no increased rates of spontaneous somatic reversion of inherited mutations, a rare but reported event (85-88), resulting in a selective growth advantage of corrected HSCs, hematopoiesis in patients with DBA will continue to rely on HSPC with the underlying genetic defect. Therefore, it is likely that patients with DBA will require continuing or repeated EPAG treatments to improve their anemia. Yet, the lowest dose and shortest exposure able to improve cytopenias into a safe range would be the goal for EPAG therapy in this patient population. Based on the response kinetic of our previous (52, 53) and ongoing EPAG studies in patients with refractory aplastic anemia (13-H-0133, NCT01891994), we hypothesize that 6 months of EPAG treatment will be sufficient to assess for a clinically meaningful response also in DBA patients.

Thus, in this study, to determine the lowest optimal dose of EPAG in patients responding to the drug, we plan a slow taper of EPAG in robust responders or subjects who reach steady state response defined as stable counts for 6 months (see §5.3, Table 3). Toxicity and efficacy data will continue to be collected during that time to help identify the secondary endpoints of duration of response, progression to clonal hematopoiesis, and toxicities with extended duration of therapy.

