# 3. Study Design

The study is designed as a single-site, non-randomized, single-arm pilot study of the oral TPOR agonist eltrombopag (EPAG) in Diamond-Blackfan anemia (Figure 3) to test the hypothesis: *eltrombopag improves the production of red blood cells in Diamond-Blackfan anemia patients.* The primary endpoint (see §8.2) is measured at 6 months (24 weeks ± 14 days). Subjects who cannot tolerate the medication or fail to respond by the primary endpoint will be taken off study drug. Subjects who *respond* at the primary endpoint (hemoglobin increase of 1.5 g/dL or more and/or transfusion independence for the previous 8 weeks, see §8.2.1) will be able to continue EPAG on the extension part of this protocol for an additional 3 years. During the 3-year extension phase, subjects will remain on the same dose of EPAG until they reach a *robust response* (defined as hemoglobin ≥10 g/dL in the absence of transfusions for more than 8 weeks, see §8.2.1). Drug dose will then be tapered slowly to the lowest dosage that maintains a stable hemoglobin (≥ 10 g/dL) and eventually discontinued if possible (per §5.3), until they meet off study criteria (see §8.6), or the study is closed. Drug will be restarted during extension if robust response is lost (*i.e.* hemoglobin falls below 9 g/dL).

Up to 30 subjects (18 for Stage 1 & 12 for Stage 2) will be screened to accrue 25 eligible subjects for this study.

[figure not shown]

Figure 3: Study enrollment and treatment schema

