# Table 2: Criteria for the adjustment of the daily dose of eltrombopag

## 5.3. Taper of eltrombopag in the extension protocol

Once a robust blood count recovery occurs in the extension part (*i.e.* hemoglobin >10 g/dL in the absence of transfusions for more than 8 weeks), EPAG dose will be tapered according to Table 3. If hemoglobin falls to <9 g/dL or the patient again requires RBC transfusions then EPAG will be either re-initiated or the dose will be increased to the last effective strength.

Age group	Starting dose	Step 1	Step 2	Step3	Step 4
		Non-Asia	an		
≥12	150 mg	75	37.5	25	stop
6-11	75 mg	37.5	25	12.5	stop
2-5	2.5 mg/kg	1.25mg/kg	stop		
East Asian, South East Asian					
≥12	75 mg	37.5	25	12.5	stop
6-11	37.5 mg	25	12.5	stop	
2-5	1.25 mg/kg	stop			

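### Section 2.4.6 plans a taper for stable responders whom Sections 3, 5.3 and 6.5.2 leave out, and at hemoglobin 9.0–9.9 g/dL the Section 3 taper target and the Section 5.3 steps diverge

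*Combined protocol and SAP*

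**What the plan says.** Section 2.4.6 gives the purpose of the taper as "to determine the lowest optimal dose of EPAG in patients responding to the drug" and continues: "we plan a slow taper of EPAG in robust responders or subjects who reach steady state response defined as stable counts for 6 months". It points to Section 5.3 and Table 3 for the details.

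Section 5.3 starts the taper as follows: "Once a robust blood count recovery occurs in the extension part", which it spells out as "hemoglobin >10 g/dL in the absence of transfusions for more than 8 weeks". It gives no second route based on a period of stable counts.

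Section 3 says: "During the 3-year extension phase, subjects will remain on the same dose of EPAG until they reach a" robust response. It continues: "Drug dose will then be tapered slowly to the lowest dosage that maintains a stable hemoglobin (≥ 10 g/dL"), with discontinuation if possible, following Section 5.3. The same paragraph restarts drug when the robust response is lost, which it equates with hemoglobin below 9 g/dL.

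Section 5.3 reverses the taper on this condition: "If hemoglobin falls to <9 g/dL or the patient again requires RBC transfusions". Table 3 lists the steps, each of 8 weeks, ending in stop.

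Section 6.5.2 sets the off-drug follow-up only for subjects whose taper followed a robust response. Section 5.6 adds no taper criterion and refers to Sections 5.2 to 5.4.

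**The concern.** Two questions get different answers depending on the section read: which responders are tapered, and what hemoglobin a lower dose has to hold.

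The first decides whether a stable, non-robust responder stays at full dose for up to three years or is stepped down. The second decides what happens to a robust responder who settles between 9 and 10 g/dL during the taper.

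Section 2.4.6 itself says that data collected over this period serve the secondary endpoints of duration of response and toxicity with longer treatment. Section 8.2.2 lists relapse in the extension phase and extended-therapy toxicity as endpoints. If exposure and loss of response follow different rules in different subjects, summaries of these endpoints mix the rules.

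**Working it through.** The plan states no figure on this point, so the check is a comparison of the text with simple arithmetic.

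**1. Who is tapered**

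| Section | Taper entry | Everyone else |
|---|---|---|
| 2.4.6 | Robust response, or six months of stable counts | Not stated |
| 3 | Robust response (≥10 g/dL, no transfusion for more than 8 weeks) | Same dose |
| 5.3 | Robust recovery (>10 g/dL, no transfusion for more than 8 weeks) | No taper route |
| 6.5.2 | Follow-up written only for taper after robust response | Not covered |

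Section 8.2.1 also sets robust response above 10 g/dL, and it alone requires two consecutive values at least 2 weeks apart. A value of exactly 10 g/dL is thus robust under Section 3 but not under 5.3 or 8.2.1.

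**2. Whether a group falls between the rules**

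Section 8.2.1 counts as response a rise of more than 1.5 g/dL from a pretreatment value below 9 g/dL, or a cut of at least 50% in transfused units over 8 weeks. Section 3 paraphrases the transfusion limb more strictly but refers to 8.2.1, so 8.2.1 is used here.

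A minimal hemoglobin responder reaches about baseline + 1.5 g/dL:

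- Baseline below 7.5: still below 9 (for example 7.0 + 1.5 = 8.5).
- Baseline 7.5 to below 8.5: 9 to below 10 (8.0 + 1.5 = 9.5).
- Baseline 8.5 to below 9: 10 or more (8.5 + 1.5 = 10.0).

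Minimal responders from any baseline below 8.5 g/dL are therefore not robust. A transfusion-limb responder who is still transfused is not robust either. If counts stay stable for six months, Section 2.4.6 tapers these subjects, while Sections 3 and 5.3 do not.

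**3. What a lower dose must hold**

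| Hemoglobin during taper, no transfusion | Section 3 target (≥10) | Section 3 restart (<9) | Section 5.3 reversal (<9) |
|---|---|---|---|
| 10 or more | Met | No | No |
| 9.0–9.9 | Missed | No | No: Table 3 continues |
| Below 9 | Missed | Yes | Yes |

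The restart columns agree. The middle row is where the sections part: the dose is too low for the Section 3 target, yet nothing in Section 5.3 halts the next step.

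**4. How fast the difference builds up**

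Table 3 has three reduced levels for non-Asian subjects aged ≥12 and 6–11 and for East or South East Asian subjects aged ≥12: 3 × 8 = 24 weeks from first reduction to stop. A subject leaving Step 1 in these groups is at stop after 2 × 8 = 16 weeks. The East or South East Asian 6–11 group has 2 × 8 = 16 weeks and the non-Asian 2–5 group 1 × 8 = 8 weeks. The East or South East Asian 2–5 group has no intermediate level.

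**5. Extreme exposure contrast under the two entry rules**

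Take a non-Asian subject aged ≥12 with a stable non-robust response:

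- Never tapered: 150 mg × 1,095 days = 164,250 mg.
- Tapered after six stable months counted from the start of the extension: 150 × 183 = 27,450 mg, plus 56 × (75 + 37.5 + 25) = 7,700 mg, total 35,150 mg.
- Ratio: 164,250 / 35,150 = 4.7.

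This assumes an uninterrupted taper to zero with no return to drug in one case, and no dose reduction for any reason in the other.

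**6. How many subjects**

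If all 25 accrue and the response rate is the 30% of the design alternative, 25 × 0.30 = 7.5 responders would be expected. The plan does not give the non-robust share or the share who would settle at 9.0–9.9 g/dL.

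**The case against.** The strongest reply is that the operative sections agree with each other. Sections 3, 5.3 and 6.5.2 all taper robust responders only, Section 5.6 sends taper decisions to the treatment plan, and the differing clause sits in a rationale that itself defers to Section 5.3. Staff following the treatment plan have one entry population. This limits the practical risk, but Section 2.4.6 states a plan and cites a section that does not contain it.

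On the thresholds, 10 g/dL may be meant as the taper target and 9 g/dL as the restart trigger. That reading is coherent, and a reader who infers opposed restart rules goes too far, because both sections use 9 g/dL. But the two-level reading is not written down, and no section says what to do between the levels.

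Several other stronger readings are tempting and fail:

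- *A stated study aim cannot be answered.* Finding the lowest dose appears in Section 2.4.6 and as a taper goal in Section 3. It is not an objective in Sections 1 or 8.1, nor an endpoint in 8.2.
- *Non-robust responders give no dose information.* Table 2 reduces the dose for high platelet counts in any subject.
- *A tapered non-robust responder would meet the reversal trigger at once.* Non-transfused responders at 9 to below 10 g/dL do not, and the trigger is worded as a fall or a renewed need.
- *Exposure would differ 4.7-fold.* That needs a completed taper with no reversal, whereas Section 2.4.6 itself expects patients to need continuing or repeated treatment. Platelet- and liver-driven reductions would also lower the full-dose total.
- *Sites would apply different thresholds.* This is a single-site study.

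**Conclusion.** The point holds as two inconsistencies in the current text: a steady-state taper route that exists only in Section 2.4.6, and no agreed rule for 9.0–9.9 g/dL during the taper. The small mismatch between ≥10 and >10 g/dL for robust response adds to the second.

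The 6-month primary response analysis is untouched, because the taper begins only in the extension. The effect is on extension-phase exposure, on extended-therapy toxicity, and on relapse, which Section 8.2 lists without defining. For robust responders a relapse date could be read at 9 or at 10 g/dL, although Section 3 leans to 9 by equating loss of robust response with a fall below it. For other responders in the extension neither level is stated to apply.

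The size cannot be estimated from the documents. The 4.7-fold ratio is an extreme contrast for one age and dose group under the assumptions shown, not an expected effect. With at most 25 subjects treated and only responders continuing, a few subjects handled differently could still change the secondary summaries. The correction is worth making but is not critical.

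**What to change.** Reconcile Sections 2.4.6, 3, 5.3 and 8.2.1 so that they share:

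1. One taper-entry condition, with one definition of robust response.
2. One condition for a tapered dose no longer maintaining the response, stating explicitly what applies at 9.0–9.9 g/dL.

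Which conditions these are is a clinical decision for the sponsor; this review takes no position on it. Then define relapse in Section 8.2.2 on the second condition and say which extension subjects it covers. If only robust responders are to be tapered, restrict the lowest-dose statement in Section 2.4.6 to them.

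The cost is a wording amendment. No visits or tests are added, since blood counts are already taken every 4 weeks on drug in the extension (Section 6.5). The one downside is that the lowest-dose statement may become narrower.
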